9.4.2 Analysis of Stool Samples

Sequence reads from shotgun metagenomic sequencing will be subjected to quality control, taxonomic assignment, gene function analysis, and metagenomic assembly using the Sunbeam metagenomics pipeline, which was co-written by CHOP Microbiome Center researchers.

The FMT inoculum will be sequenced alongside fecal samples collected from subjects before and after the FMT procedure. DNA sequence reads from the inoculum will be assembled into contigs (overlapping DNA segments) using MEGAHIT (Li Bioinformatics, 2015). The metagenomic contig sequences represent segments of bacterial genomes from the microbiota. We will identify protein coding genes in the contig sequences, and use this gene set as unique identifiers for the genomes in the inoculum. Reads from patients before and after FMT will be aligned to the inoculum marker gene sequences. Gene sequences which are present in patients before the transplant will be removed from the set of inoculum marker genes. The percentage of total non-human reads aligning to the inoculum marker gene set will be used as a measure of bacterial engraftment following FMT.

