1 STUDY SUMMARY

1.1 Synopsis Title: Fecal Microbial Transplantation (FMT) For the Treatment of Fecal Incontinence in Women FMT for FI **Short Title:** Open label pilot study assessing FMT to treat fecal incontinence in Study women > 50 years of age. **Description: Objectives:** The primary objective is to determine if fecal microbial transplantation leads to clinical improvement in fecal incontinence. Change in the St. Mark's Vaizey score, a measure of fecal incontinence Primary severity, 4 weeks after FMT. **Endpoint:** Secondary Determine whether the effectiveness of microbial engraftment following **Endpoints:** fecal microbial transplantation is associated with the degree of clinical improvement. Determine whether the baseline microbiota configuration affects engraftment in fecal microbial transplantation for fecal incontinence. Our working hypothesis is that the transplant will be more effective in baseline samples with lower microbial diversity. 15 evaluable women, > 50 years of age, who have been diagnosed with Study **Population:** fecal incontinence and have failed standard treatment. 1/2Phase: **Description of** Penn Medicine - University of Pennsylvania Health System Sites/Facilities Participants will be enrolled form the Urogynecology clinics at the Enrolling University of Pennsylvania. **Participants: Description of** Participants will undergo fecal microbial transplantation (FMT) using the Penn Microbiome Therapy – 002 (PMT-002): no more than 152 mL Study **Intervention:** suspension for intragastric or intraduodenal administration from 40g human stool, comprising $1 \times 10^8 - 1 \times 10^{12}$ anaerobic bacterial CFUs/dose. **Study Duration:** 24 months **Participant** Approximately 8 months **Duration:**

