3 STUDY OBJECTIVES AND ENDPOINTS

OBJECTIVES	ENDPOINTS
Primary	
Determine if fecal microbial transplantation leads to clinical improvement in refractory fecal incontinence in older women.	Number of subjects that show significant improvement at 4 weeks after FMT, and will be maintained at 12 weeks, relative to baseline using the St. Mark's Vaizey score, a measure of fecal incontinence severity.
Primary Safety	
Determine the safety of FMT administration via naso-gastric tube in older women with FI.	Frequency of adverse events, serious adverse events, and adverse events of special interest (including allergic reaction and gastrointestinal symptoms).
Secondary	
Determine if FMT leads to improved quality of life for subjects.	Number of subjects that have an improved quality of life at 4 and 12 weeks, measured by the FIQL scale.
Determine if the effectiveness of microbial engraftment following fecal microbial transplantation is associated with the degree of clinical improvement.	Concentration of microbiota present at baseline vs. at week 4 and at 12 weeks (optional)in subjects that demonstrate a significant improvement at 4 weeks after FMT, relative to baseline using the St. Mark's Vaizey score.
Tertiary	
Determine whether the baseline microbiota of the subject affects engraftment in fecal microbial transplantation for fecal incontinence.	Concentration of microbiota at baseline vs. concentration of microbiota at 4 weeks and at 12 weeks (optional).

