9.2 Primary	
Determine if fecal microbial transplantation leads to clinical improvement in refractory fecal incontinence in older women.	Our working hypothesis is that the St. Mark's Vaizey score, a measure of fecal incontinence severity, will significantly improve at 4 weeks after FMT, and will be maintained at 12 weeks, relative to baseline. A secondary outcome will be quality of life at 4 and 12 weeks.
Primary Safety	
Determine the safety of FMT administration via NG tube in older women with FI.	Our hypothesis is that there will be low occurrence of serious adverse events following administration of FMT via NG tube.
Secondary	
Determine whether the effectiveness of microbial engraftment following fecal microbial transplantation is associated with the degree of clinical improvement.	Our working hypothesis is that more transplanted strains will be present at 4 weeks in subjects with a higher response score.
Tertiary	
Determine whether the baseline microbiota configuration affects engraftment in fecal microbial transplantation for fecal incontinence.	Our working hypothesis is that the transplant will be more effective in baseline samples with lower microbial diversity.

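### Does the engraftment percentage in section 9.4.2 need rescaling before it is related to baseline diversity?

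*Combined protocol and SAP*

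**What the plan says.** Section 9.4.2 assembles the inoculum into contigs, identifies protein-coding genes and uses them as markers of the donor material. It then says: "Gene sequences which are present in patients before the transplant will be removed from the set of inoculum marker genes". The measure follows: "The percentage of total non-human reads aligning to the inoculum marker gene set will be used as a measure of bacterial engraftment following FMT". The section also commits to sequencing the product itself: "The FMT inoculum will be sequenced alongside fecal samples collected from subjects before and after the FMT procedure".

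The hypotheses table in section 9 uses engraftment twice. The secondary hypothesis is about amount: "more transplanted strains will be present at 4 weeks in subjects with a higher response score". The tertiary one is about effectiveness: "the transplant will be more effective in baseline samples with lower microbial diversity". The synopsis (section 1.1) carries the latter under its secondary endpoints. The endpoint table in section 3 describes both objectives by the concentration of microbiota at baseline and follow-up.

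Nowhere do the documents state whether genes are removed per woman or across the cohort, give a presence threshold, or name a diversity index or a test for the diversity objective.

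**The concern.** The removal step ties the yardstick to the woman's own baseline. If each woman's pre-existing genes are struck from her own marker set, a woman who already carries much of the inoculum has few markers left and can score only a low percentage, however well the rest takes. A woman with a sparse baseline community may have more markers left and more room to score.

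The plan predicts better engraftment at lower diversity, and this lean runs the same way. Subtracting the baseline percentage would not help, because under per-woman removal it is near zero by construction. A raw association could then be read as better take in low-diversity women and carried into planning of the later randomised trial, which is the pilot's stated purpose. Engraftment is also described in three ways (read percentage, strains present, concentration), so it is fair to ask which quantity is meant.

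**Working it through.** **The plan's own engraftment figure.** Section 9.3 gives a detectable difference of 1.59 SD with 15 women and a response rate near 60%, that is 9 responders and 6 non-responders. A two-sample t-test with two-sided 5% alpha and 80% power (both assumed, as neither is stated) gives 1.598 SD, and power at 1.59 SD is 79.6%. The figure reproduces. It concerns responders against non-responders and does not depend on the present point.

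**Mechanism.** Under per-woman removal, roughly:

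raw percentage = take × (1 − overlap)

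where overlap is the share of the inoculum already carried. With take 0.30 in both women (assumed):

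- overlap 40%: 0.30 × 0.60 = 18%
- overlap 70%: 0.30 × 0.30 = 9%

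Dividing by the remaining share gives 18/0.60 = 30% and 9/0.30 = 30%. One number cannot identify two factors, so the algebra of the concern is right.

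**How large.** The documents give no overlap, take or test, so every input is assumed. The first model has 15 women, 200 donor species with lognormal abundance (log-SD 1.5), 0–150 non-donor species, mean take about 0.3 varying between women (logit SD 1), take unrelated to diversity, and a Spearman test. It counts spurious results in the hypothesised direction (nominal 2.5%):

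| Overlap range | Raw | Mean raw rho |
|---|---|---|
| 30–80% | 11.1% | −0.21 |
| 40–70% | 5.1% | −0.09 |
| 50–70% | 3.9% | −0.06 |

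The scaled percentage gives 2.4–2.6% throughout. With overlap unrelated to diversity, raw is 2.4–2.7%. With pooled removal it is 1.8–2.8%.

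A second, simpler model ties overlap closely to diversity and lets take vary less (log-SD 0.3 or 0.5). Against a two-sided 5%, raw gives 22.7% / 12.6% at overlap 40–60%, 66.2% / 32.8% at 30–70% and 90.9% / 62.8% at 20–80%. Scaled gives 5.0–6.1%. The spread between the two models shows that the direction is established only under the premises, and the size not at all.

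**Which removal unit would an analyst use?** If 15 women each carried an independent half of the donor genes, pooled removal would leave 0.5^15, about 0.003% of the set. Under less extreme simulated prevalence, pooling leaves 57–93% of engrafted donor abundance uncounted. Section 4.1 also refers to donors in the plural, so the inoculum may differ between women. Per-woman removal is the workable reading.

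**Does scaling settle the question?**

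- *Units.* The planned numerator is a share of the recipient's reads; the proposed denominator is a share of inoculum reads. They match only if species keep their donor abundances in the recipient. With an assumed lognormal shift (log-SD 1 or 2), the ratio exceeds 1 in 1.4% or 9% of women, and the null scaled rho is −0.09 or −0.10.
- *Target.* If newly acquired donor share is what matters and is unrelated to diversity, scaling creates a false positive association: rho +0.04 to +0.67, significant in 3–84% of trials.
- *Detection.* If 10–30% of resident species are missed at random at baseline, scaled rho drifts to between +0.03 and +0.23.
- *Discrimination.* In the first model, among null trials where raw happens to be significant, scaled rho still averages −0.38 to −0.51. It falls below half of raw in only 27%, 6% and 3% of them across the three overlap ranges. A drop of more than 0.1 occurs in 80%, 53% and 41% of those trials, but also in 53%, 29% and 22% when take truly falls with diversity.

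**The case for a change.** The strongest case for a change is that it costs almost nothing. The inoculum is sequenced anyway, the raw analysis would stay, and one extra column would show how much of the donor set each woman had left. The removal unit affects the result under either reading, so it is better fixed before data are seen. The word effective in the tertiary hypothesis can be read as take per available gene, and on that reading the raw percentage alone is incomplete.

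Much of this stands. The text does leave the removal unit open, the three descriptions of engraftment do not match, and under the two premises the raw percentage mixes take with room to score. What does not stand is the step to a needed correction. No section asks for take per available gene; that is a different estimand. If low diversity helps because more donor organisms are absent, low overlap is part of the hypothesised effect, and dividing by the remaining share would remove it. The second column would also rarely change a reader's conclusion with 15 women.

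**Conclusion.** No change to the plan is called for. Section 9.4.2 names an operational measure, and it is valid for newly acquired donor share, the reading closest to the secondary hypothesis and a natural one for the tertiary. The unstated removal unit is missing detail with one workable answer: remove genes per woman, against the product she received. The mismatch with the concentration wording in section 3 is a drafting inconsistency.

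The lean towards the hypothesis needs both per-woman removal and lower overlap at lower diversity. The second premise is plausible but appears nowhere in the documents, and the size runs from negligible to large depending on assumed inputs. The conclusion therefore does not rest on the effect being small. It rests on the stated measure being legitimate, on scaling being a debatable alternative with biases of its own, and on the stakes: an exploratory association in 15 women, listed as tertiary in sections 3 and 9 and secondary only in the synopsis, with no planned test and no decision attached. Ordinary care in reporting is enough: an association between the raw percentage and diversity describes donor material gained and should not be presented as better take per available donor gene.

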4 STUDY PLAN

4.1 Study Design

Traditional treatments of fecal incontinence directed at obstetric neuromuscular injury, such as pelvic floor exercises and sphincteroplasty, have remarkably low efficacy in older women. The proposed study will provide critical feasibility and safety data for conducting a future randomized clinical trial of FMT versus placebo for the treatment of refractory fecal incontinence. We plan a single arm open label clinical trial of FMT for the treatment of refractory fecal incontinence. Older women with fecal incontinence who have failed prior treatment with diet modification and pelvic floor exercises will be invited to participate in the study. Penn Microbiome Therapy – 002 (PMT-002), which is derived from healthy screened donors will be delivered to the duodenum via a nasogastric tube. All subjects will complete validated questionnaires on fecal incontinence and contribute a stool sample for microbiota analysis at baseline and at 4 and 12 weeks after the FMT procedure.

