9.1 Statistical Hypotheses

9.3 Sample Size Determination

Initial open label clinical trials of FMT for irritable bowel syndrome were performed with 10-15 patients. (Holvoet, Gut 2017; Pinn ,Am J Gastro, 2014; Mazzawi, PLoS One, 2018) In the proposed pilot study, we will examine 15 evaluable women with refractory fecal incontinence to gather essential feasibility and outcomes data to conduct a future RCT of FMT. In a prior study of 13 adults with irritable bowel syndrome, significant differences in signals for several bacteria (*Bacteroides, Desulfitispora, Bifidobacteria*) were noted between 8 responders and 5 non-

responders to FMT (response rate 60%). (Mazzawi PLoS One, 2018) If the response rate is near 60% in our pilot study, we will be able to detect a difference in bacterial engraftment of 1.59 standard deviations. Our power will be decreased if the response rate is either very low (<3) or very high (>12). With 15 subjects in a single arm study, the response rate will be determined to within 10% (interquartile range).

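### The engraftment percentage in section 9.4.2 has no background estimate: a positive value alone does not show donor engraftment, and its floor moves with baseline read depth and gene richness

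*Combined protocol and SAP*

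**What the plan says.** Section 9.4.2 sets out the samples and the measure:

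- Samples: "The FMT inoculum will be sequenced alongside fecal samples collected from subjects before and after the FMT procedure".
- Alignment: "Reads from patients before and after FMT will be aligned to the inoculum marker gene sequences".
- Removal: "Gene sequences which are present in patients before the transplant will be removed from the set of inoculum marker genes".
- Measure: "The percentage of total non-human reads aligning to the inoculum marker gene set will be used as a measure of bacterial engraftment following FMT".

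The section gives no read depth and no number of reads that makes a gene present. It does not say whether removal is done woman by woman or over all women together, and it subtracts no background.

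The design offers no other source of background. Section 4.1 states "We plan a single arm open label clinical trial of FMT for the treatment of refractory fecal incontinence", and each woman is to "contribute a stool sample for microbiota analysis at baseline and at 4 and 12 weeks after the FMT procedure", so there is no untreated arm and no second pre-treatment sample. Section 9.3 plans that "we will examine 15 evaluable women with refractory fecal incontinence".

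Engraftment enters two objectives. The secondary one relates it to clinical response. The tertiary one relates it to baseline microbiota, with the hypothesis in section 9 that the transplant works better where baseline diversity is lower. The secondary endpoint in section 3 is worded "Concentration of microbiota present at baseline vs. at week 4", with an optional week-12 sample.

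**The concern.** The rule treats a single baseline stool as a complete list of what the woman carried. It is a finite sample of reads, so rare genes are missed. If such a gene is also in the inoculum it stays in the marker set, and any later read from it counts as donor material. A common gene gained from food or contacts between visits counts the same way.

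Baseline reads define the removal, so the baseline value is held at or near zero while the follow-up value is not. The measure therefore has a positive floor that is unrelated to the transplant. That floor depends on how deeply the baseline sample was sequenced and how many genes it held. The first is a laboratory accident. The second is close to the explanatory variable of the tertiary analysis.

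At stake is whether this pilot can say that donor bacteria took hold, and at what level, before a randomized trial is built on it.

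**Working it through.** **The plan's own figure.** Section 9.3 gives a detectable engraftment difference of 1.59 SD at a response rate near 60%, that is 9 responders and 6 non-responders. The test, alpha and power are not stated. I assume a two-sample t-test, two-sided 0.05 and 80% power. The noncentrality is d × √(9×6/15) = 1.897d on 13 degrees of freedom. Power at d = 1.59 is 79.6%, and 80% is reached at 1.598. The figure reproduces.

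**One gene.** Let λ be its expected reads in each sample, with unchanged abundance and no transfer. Under a one-read rule, P(missed at baseline) = e^−λ, and P(missed, then counted as engraftment) = e^−λ(1 − e^−λ).

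| λ | missed | falsely counted |
|---|---|---|
| 0.5 | 61% | 24% |
| 1 | 37% | 23% |
| 3 | 5.0% | 4.7% |
| 5 | 0.7% | 0.7% |

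**Whole sample, no transfer.** All inputs here are assumptions: 200,000 genes, log-normal abundance with log-SD 2.5, half of the woman's genes also in the inoculum, Poisson reads, 5 million follow-up reads, one-read rule, removal per woman. The baseline value was 0% in every run, and all 15 simulated women were above zero at follow-up. Mean follow-up share:

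| Baseline reads | same composition | log-abundance correlation 0.95 | correlation 0.8 |
|---|---|---|---|
| 0.2M | 4.5% | 5.5% | 9.6% |
| 1M | 1.3% | 1.7% | 3.6% |
| 5M | 0.28% | 0.39% | 0.96% |
| 20M | 0.06% | 0.08% | 0.24% |

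Repeat runs of the top left cell gave 4.5% to 4.6%. Newly acquired species are not modelled and would add to these values.

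**Richness at equal depth (1M reads, same composition).** With 100,000, 200,000 and 400,000 genes the false share is 0.71%, 1.33% and 2.35%. It rises with richness, so here it runs against the tertiary hypothesis and could hide a true effect.

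**Unstated choices.** I varied the model so that gene prevalence differs between women, with correlation 0.95.

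- Removal per woman gives 0.92%, 0.19% and 0.03% at 1M, 5M and 20M reads. Pooled removal over 15 women gives 0.039%, 0.003% and 0.0004%.
- With a three-read threshold, per woman at 5M, the baseline value is 0.28% and the follow-up value 0.60%. The baseline is no longer exactly zero, but the rise remains.

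**Effect on the responder comparison.** A floor common to all women leaves the type I error at 4.8% (4,000 runs). Unequal depth does not cancel. With mean baseline depth near 5M reads and a coefficient of variation of 0.6, the no-transfer values of 15 women ran from 0.12% to 1.43% (SD 0.35 percentage points, against 0.01 at equal depth). If such noise cut reliability to 0.8, an assumed value, the standardised difference becomes 1.59 × √0.8 = 1.42 and power falls from 80% to 70%. The detectable true difference becomes 1.598/√0.8 = 1.79 SD.

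**Would a control marker set work?** A mismatched set with the same removal and the same overlap gave 1.34% against 1.33% at 1M reads, and 3.61% against 3.62% at correlation 0.8. The difference is about zero, as it should be. There are three cautions:

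- Overlap must match. Control overlaps from 20% to 70% gave 0.5% to 1.9% against a floor of 1.3%.
- A second lot from the same donor cancels true engraftment: 7.2% minus 7.2% in one run.
- Subsampling everyone to the shallowest of 15 samples raised the mean false share from 0.28–0.40% to 0.53–1.11%.

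**The case against.** The case on the other side has real force.

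A reader might infer that the trial is bound to announce engraftment: all 15 women rise from zero, and a sign test gives 2 × 0.5^15 = 0.00006. The documents do not support that. No such test is planned. Section 3 speaks of a concentration of microbiota, and nothing says that the percentage in 9.4.2 is itself compared with its own baseline. Exact zero at baseline also needs a one-read rule, which 9.4.2 does not state.

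A reader might also infer that the responder comparison is biased upward. It is not, for a constant floor. Uneven depth is noise there unless depth is related to response, and no reason for that is apparent.

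The wording of 9.4.2 can be read as pooled removal, which makes the artefact very small, and deep sequencing has a similar effect. Removing baseline genes is itself a partial background control. It also discards donor strains that share genes with the woman's own, which lowers the measure.

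Finally, these are secondary and tertiary questions in a 15-woman pilot. The primary and safety objectives are untouched.

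All of this limits the size and reach of the point. None of it supplies a background estimate, and the plan commits neither to pooled removal nor to any depth. The dependence on richness also remains at equal depth.

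**Conclusion.** The point holds in a limited form. As 9.4.2 stands, a positive percentage does not by itself show that donor bacteria engrafted, and its absolute level cannot be read as the amount of take. Uneven baseline depth costs power in the secondary analysis. Dependence on gene richness confounds the tertiary one.

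The size cannot be derived from the documents. With a one-read rule, per-woman removal and unchanged composition, it runs from about 0.06% to 4.5% of reads for baseline depths of 20M down to 0.2M. Turnover raises it, and pooled removal nearly abolishes it. These values rest on the assumed gene count, abundance spread and 50% overlap. No true engraftment level is available to set against them. The 1.59 SD figure in section 9.3 is not in question.

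**What to change.** Amend 9.4.2 before the sequence data are analysed:

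1. State one presence threshold. Apply gene removal per woman at a common baseline read depth. Exclude or flag very shallow samples, so that the worst one does not set the common depth.
2. For each woman, build mismatched control marker sets by the same steps from other women's baseline stools. Add inocula only if they come from a different donor, never another lot from the donor she received; the documents do not say how many donors are used. Section 2.2 reports that women with this condition differ from controls in their stool bacteria, so scale or match the control sets to the received set for number of genes and for overlap with her baseline genes.
3. Report the received-inoculum value, the control value and their difference. Use the difference for any statement that engraftment occurred and in the secondary and tertiary engraftment analyses. Keep the unsubtracted percentage as a sensitivity analysis.

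The cost is computing time only, since the inoculum and all baseline stools are already to be sequenced. Engraftment figures will be lower and slightly noisier.
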